Consequently, MBSR is a potentially useful intervention to prevent psychopathological sequela of the high-stress situations that healthcare workers went through in the current COVID-19 pandemic. The aim of this study is to examine the effectiveness of an adapted MBSR intervention delivered via videoconferencing to reduce psychological distress in COVID-19 healthcare professionals.

Objectives

Primary research question:

- I. Is an adapted videoconferencing MBSR intervention + support as usual (SAU) superior to a standalone online mindfulness intervention (SOM) + SAU in terms of reducing psychological distress (measured by a compound measure of depressive, anxiety, and somatic symptoms) at 6 months after completing the intervention (= 7 months follow-up)?

Secondary research questions:

Additional outcome measures

- II.1 Is there less psychiatric psychopathology diagnosed by clinical interviews after adapted MBSR + SAU compared to SOM + SAU at 7 months follow-up?
- II.2. Is an adapted MBSR + SAU more effective than SOM + SAU in reducing psychological distress (depressive, anxiety, and somatic symptoms) and post-traumatic stress symptoms, insomnia and alcohol use over the course of 7 months after baseline?
- II.3. Is an adapted MBSR + SAU more effective than SOM + SAU in improving post-traumatic growth and positive mental health over the course of 7 months after baseline?

Moderation of the effect

II.4 Is the effect of an adapted MBSR to reduce psychological distress moderated by gender, age, work setting, profession, prior mindfulness training, adherence, baseline depressive, anxiety and somatic symptoms, and baseline perseverative thinking, mindfulness and self-compassion?

Mediation of the effect

II.5 Is the effect of and adapted MBSR and SOM + SAU to reduce psychological distress mediated by a decrease of perseverative thinking, and an increase in mindfulness skills and self-compassion?

Section 3: Study Methods

Trial design

A nationwide, parallel-group randomized controlled superiority trial is conducted comparing an adapted MBSR + SAU (intervention) with SOM + SAU (control). The intervention is an interactive adapted videoconferencing MBSR group-training. The training consists of eight 1,5 hour sessions twice a week during 4 weeks. The sessions will be held via interactive videoconferencing. Participants in the control condition will have the possibility to use a self-help daily mindfulness exercise (30 minutes) on a YouTube channel. In total the participants will receive 24 mindfulness and compassion exercises in 4 weeks. Treatment allocation is a 1:1 ratio. Assessments will be conducted at baseline (T0), mid-treatment (T1), and at 1 (T2), 4 (T3) and 7 (T4) months follow-up. Participants randomized to the SOM + SAU condition will be able to participate in an adapted MBSR intervention after they completed the study (7 months).

Randomization

Random assignment to adapted MBSR + SAU or SOM + SAU is electronically conducted by CastorEDC. Randomization is stratified by setting (3 levels: hospital, nursing home, other), prior mindfulness training (yes/no), and profession (3 levels: physician, nurse, other). Block randomization with predefined blocks are used (2 or 4) in order to ensure balanced groups. Diagnostic research assessors conducting clinical interviews were blinded to the treatment allocation.

Sample size

Based on Lai et al.[1], high post-exposure levels of depression, anxiety, insomnia and distress are expected (in 50-70% of healthcare workers). So far, no data exist on changes of these levels of distress in healthcare workers in the COVID-19 pandemic due to interventions.

Therefore, we aim to detect an effect-size of 0.4 ($\alpha=0.05$; $\beta=0.20$; two-tailed). When using t-tests, a sample size of 200 (100 in each arm) is needed. This will suffice to reveal a clinically relevant difference of 5 points on the PHQ-SADS[8] (scale of sum-score 0-78). To overcome attrition, we will increase the size of our groups with 10%. Thus, a total of 220 participants (110 in each group) will be included in this randomized controlled study.

Framework

Both primary and secondary outcomes will be assessed for superiority of an adapted MBSR + SAU above SOM + SAU.

Statistical interim analyses and stopping guidance

Not applicable

Timing of final analysis

All outcomes will be analyzed collectively after the T4 measurement and the SCID5 interviews have taken place in the last participants (anticipated being June 2022).

Timing of outcome assessments

At baseline participants complete the questionnaires used for our primary/secondary outcomes. The same questionnaire are send after 1 month (post-intervention), and after 4 and 7 months. To measure possible mediators three questionnaires are used at mid-treatment (2 weeks after start of

the intervention). At 7 months the occurrence of psychopathology is measured by the Structured Clinical Interview for DSM-5 (SCID5).

Section 4: Statistical Principles

Confidence intervals and P values

Level of statistical significance

All applicable statistical tests will be 2-sided and will be performed using a 5% significance level.

Description and rationale for any adjustment for multiplicity

Not applicable

Confidence intervals to be reported

All confidence intervals presented will be 95% and two-sided.

Adherence and protocol deviations

Definition of adherence to the intervention and how this is assessed

Adherence implies that participants attended ≥ 4 sessions in the adapted MBSR + SAU group. The MBSR trainer will keep an attendance register.

Participants in the SOM + SAU group will be asked at timepoint T1 and T2 how often they did a mindfulness exercise in the last two weeks.

Analysis populations

All analyses will be conducted in SPSS version 25 and will be performed as intention-to-treat (ITT). The intention-to-treat population will include all randomized patients, according to the treatment they were randomized to receive. Secondary, per protocol analyses will be conducted.

Section 5: Trial Population

Screening data

Potential participants fill out an online registration form expressing their interest for the study. Next, a screening interview by telephone is planned. Study information will be given and in- and exclusion criteria will be checked during this interview. All screened potential participants and their eligibility will be registered.

Eligibility

Participants are eligible if they are healthcare workers who either currently or recently have been working in the acute care for COVID-19 patients on COVID-19 wards/intensive care units or in primary care or nursing homes. The exclusion criteria are insufficient comprehension of the Dutch language, and inability to access the interactive videoconferencing. The number of ineligible participants will be reported with reasons for ineligibility. Eligible participants who refrain from participating before randomization will be reported with reasons for withdrawal.

Recruitment

A CONSORT flow diagram will be used to summarize the number of participants who were:

- Assessed for eligibility at screening
 - Eligible at screening
 - Ineligible at screening*
- Eligible and randomized
- Eligible but not randomized*
- Received the randomized allocation
- Did not receive the randomized allocation*
- Discontinued the intervention*
- Lost to follow-up*
- Randomized and included in the primary analysis
- Randomized and excluded from the primary analysis*

*reasons will be provided.

Withdrawal/follow-up

The level of consent of withdrawal will be classified as “consent to continue data collection” or “no further data collection”. The numbers (with reasons) of losses to follow-up (drop-outs and withdrawals) over the course of the trial will be summarized by intervention arm and presented in the CONSORT diagram.

Baseline patient characteristics

Participants will be described by intervention arm with respect to age, gender, marital status, having children, level of education, previous and current psychological treatment, prior mindfulness training, work setting, profession, working years in healthcare.

Categorical data will be summarized by numbers and percentages. Continuous data will be summarized by mean, SD and range if data are normal distributed and median, IQR and range if data are skewed.

Section 6: Analysis

Outcome definitions

Primary outcome

The primary outcome will be the change in psychological distress between baseline and 7 months follow-up, as assessed by the total score on the *Patient Health Questionnaire – Somatic, Anxiety and Depressive Symptoms (PHQ-SADS)*[8] scale. This is a 31-item self-report measurement combining PHQ-9, GAD-7, and PHQ-15. The 9-item *Patient Health Questionnaire (PHQ-9)*[9] evaluates the presence of the nine DSM-5 criteria of a depressive episode in the past 2 weeks: depressed mood, anhedonia, trouble sleeping, feeling tired, change in appetite or weight, guilt or worthlessness, trouble concentrating, feeling slowed down or restless and suicidal thoughts. There are four answer categories: 0 (not at all), 1 (few days), 2 (more than half the days) and 3 (almost every day). The 7-item *Generalized Anxiety Disorder (GAD-7)*[10, 11] scale measures severity of anxiety. Frequency of anxiety symptoms are rated within the last 2 weeks on a 4-point scale ranging from 'not at all' to 'almost every day'. The 15-item *Patient Health Questionnaire (PHQ-15)*[12] is a self-administered questionnaire includes 15 symptoms that account for more than 90% of all symptoms seen in primary care. Subjects were asked for the last 4 weeks to rate the severity of 15 symptoms as 0 (not bothered at all), 1 (bothered a little), and 2 (bothered a lot).

Cut-off scores of ≥ 5 , ≥ 10 , and ≥ 15 representing mild, moderate, and severe symptoms, respectively, on all three scales. The total score of the PHQ-SADS will be calculated by the sum of PHQ-9, GAD-7 and PHQ-15, and ranges from 0 to 78.

Confirmatory factor analysis will be performed, in line with the research on the PHQ-ADS[13], to investigate sufficient unidimensionality of the PHQ-SADS to support the use of the total score as a composite measure for depression, anxiety and somatic symptoms.

Secondary outcome

The *Structured Clinical Interview for DSM-5 Axis I Disorders Research Version (SCID5)* will be used to retrospectively assess the occurrence of psychopathology (depression, anxiety disorder, posttraumatic stress disorder (PTSD), insomnia, substance abuse, somatoform disorder, obsessive compulsive disorder, eating disorder, illness anxiety disorder, adjustment disorder) at 7 months follow-up. The psychometric properties of the Dutch translation of the SCID have been shown to be excellent.[14] The SCID-5 will provide dichotomous score (presence or absent of psychopathology).

The *Posttraumatic Stress Disorder Checklist for DSM-5 (PCL-5)*[15] is a 20-item self-report measure that assesses the 20 DSM-5 symptoms of PTSD. The PCL-5 demonstrated excellent reliability and validity.[16]

The *Insomnia Severity Index (ISI)* is a 7-item scale assessing global insomnia. Total scores range from 0 to 28 with higher scores indicating greater severity.[17, 18]

The *AUDIT-C (Alcohol Use Disorders Identification Test)*[19] is a 10-item, effective method of screening for unhealthy alcohol use, defined as risky or hazardous consumption or any alcohol use disorder.

The *Mental Health Continuum – Short Form (MHC-SF)*[20] will be used to assess emotional, psychological, and social well-being. The MHC-SF is a 14-item measure with a total score range of 0 to 70. The psychometric properties of the MHC-SF have been shown to be adequate.[20]

The degree of posttraumatic growth will be measured with the *Posttraumatic Growth Inventory – Short Form (PTGI-SF)*. [21] The PTGI-SF measures the general tendency to experience difficult events in such a way that benefits are perceived. The measure consists of 10 items. The psychometric properties of the PTGI-SF have shown to be adequate.

The *Five Facet Mindfulness Questionnaire – Short Form (FFMQ-SF)* [22], a 24-item questionnaire, will be used to assess different aspects of mindfulness, including observing, describing, acting with awareness, non-judging of inner experiences, and non-reactivity to inner experiences. The psychometric properties of the FFMQ-SF have been shown to be adequate.

The *Self Compassion Scale – Short Form (SCS-SF)* [23] will be used to assess levels of self-compassion. The SCS-SF is a 12-item measure that consists of three concepts that are related to self-compassion, including self-kindness versus self-judgment, common humanity versus isolation, mindfulness versus over-identification. The psychometric properties of the SCS-SF have been shown to be adequate. [23]

The *Perseverative Thinking Questionnaire (PTQ)* [24] consists of 15 items and will be used to assess repetitive negative thinking (RNT). The PTQ comprises of three core characteristics of repetitive negative thinking (repetitiveness, intrusiveness, and difficulties to disengage) and two associated features (unproductiveness of RNT and RNT capturing mental capacity). The psychometric properties of the PTQ have shown to be adequate. [24]

The Trimbos/iMTA questionnaire for Costs associated with Psychiatric illness (TiC-P) [25] will be used to collect information on direct healthcare use and paid and informal work-related productivity losses at 7 months. The EuroQol-5D-3L (EQ-5D) will be used to measure health-related quality of life.

COVID-19 related questions and mindfulness practice questions will be asked.

Analysis methods

Treatment effects at T4

Primary analyses will be performed on the intention-to-treat (ITT) sample. ANCOVA will be used to examine the main effect (PHQ-SADS) of the intervention at T4. Roughly, every month during approximately one year a group will start with the intervention (cohort). Due to the expected differences in these groups, cohort effects will be added. Therefore, a Linear Mixed Effect Model will be used for the analyses. Group (adapted MBSR + SAU / SOM + SAU) will be added as fixed effects, while controlling for baseline levels. A random effect for cohort will be added, and if applicable as a fixed effect. Cohen's *d* effect size will be calculated by dividing the adjusted group difference at T4 by the pooled standard deviation at T0. [26]

Difference in occurrence of psychopathology (present/absent) between adapted MBSR + SAU and SOM + SAU assessed by SCID-5 interview at T4 will be tested with Chi-square test.

Course to treatment effect at T4

The course of treatment effects from baseline to T4 for both primary and secondary outcomes (post-traumatic stress symptoms, insomnia, alcohol use, post-traumatic growth, positive mental health) at

T2, T3, and T4 will be evaluated with Linear Mixed Effects Models. Time, group (adapted MBSR + SAU / SOM + SAU) and their interaction will be added as fixed effects, while controlling for baseline levels. A random effect for participant and cohort (random slope and intercept) will be added. Heterogeneous first-order autoregressive (ARH(1)) covariance structure will be used, which assumes that measurements closer in time are more strongly related to each other. Restricted maximum likelihood will be used as estimation method to handle missing data. Cohen's *d* effects size will be calculated by dividing the adjusted group difference between the pooled means (T2, T3, T4) by the pooled standard deviations at T0.[26]

Moderation of the effect

Moderation will be examined by adding the potential moderator and its interaction with group to the model. Separate models will be run for each possible moderator. The following possible moderators will be used: gender, age, work setting, profession, prior mindfulness training, adherence, baseline depressive, anxiety and somatic symptoms, and baseline perseverative thinking, mindfulness and self-compassion.

Mediation of the effect

Mediation analysis will be performed on per-protocol sample, using the multiple mediation model by Preacher & Hayes.[27] We will examine whether T0 to T1 change in potential mediators (mindfulness skills, self-compassion, and perseverative negative thinking) mediated T0 to T2 change in depressive, anxiety and somatic symptoms, post-traumatic stress symptoms, insomnia, post-traumatic growth and positive mental health.

Any adjustment for covariates

See above

Methods used for assumptions to be checked for statistical methods

Assumptions of normality will be checked and, in case of lack of normality, bootstrapping will be used to account for this problem.

Any planned sensitivity analyses for each outcome

Sensitivity analyses will be conducted by performing the primary and secondary analyses in the per-protocol (PP) sample. The per-protocol analysis set consists of subjects who have a minimum exposure of 4 MBSR sessions (intervention group (adapted MBSR + SAU)). Further sensitivity analysis will be performed depending on possible patterns in missing values and when relevant disbalance in covariates will be observed.

Any planned subgroup analyses for each outcome

Moderation will be examined by adding the potential moderator and its interaction with group to the model. Separate models will be run for each possible moderator. The following possible moderators

will be used: gender, age, profession, work setting, prior mindfulness training, baseline levels of depressive, anxiety and somatic symptoms.

Missing data

No imputation will be needed for baseline measures, because participants were only randomized if T0 was completed. The questionnaires will be filled in an online platform (CastorEDC), in which it is required to fill in an item before continuing to the next item. Therefore, we expect a low number of missing data.

Additional analysis

None

Harms

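### The SCID-5 outcome has no look-back start, so as written it can count disorders that ended before randomisation, and its test ignores baseline

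*SAP*

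**What the plan says.** Question II.1 in the SAP's Objectives reads: "Is there less psychiatric psychopathology diagnosed by clinical interviews after adapted MBSR + SAU compared to SOM + SAU at 7 months follow-up". This is a comparison after the intervention, at a stated time.

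The outcome definition (Section 6, Outcome definitions, Secondary outcome) says the SCID-5 will "retrospectively assess the occurrence of psychopathology" at 7 months, across ten disorder groups, giving one binary score. No section gives a start to the look-back, a rule on onset, or a distinction between current and past disorder.

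Three further places bear on this:

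- Section 3, Timing of outcome assessments: "At baseline participants complete the questionnaires used for our primary/secondary outcomes". The SCID-5 appears only at 7 months.
- Section 5, Eligibility: "The exclusion criteria are insufficient comprehension of the Dutch language, and inability to access the interactive videoconferencing". An existing or past disorder does not bar entry.
- Section 6, Analysis methods, Treatment effects at T4: the difference in occurrence, "assessed by SCID-5 interview at T4 will be tested with Chi-square test". No covariate enters this test, whereas the models for the continuous outcomes control for baseline level.

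**The concern.** The outcome definition describes a period of unstated length, whereas the research question and the test refer to a state at 7 months. The same interview can give different event counts under the two.

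Taken literally, the definition has no lower limit. A participant whose only depressive episode began and ended before randomisation could score as present. Treatment cannot change that score, so each such person adds an event that carries no information about the intervention. Without a baseline interview, only dating of episodes at the 7-month interview can separate these cases, and the SAP sets no rule for using it.

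The SCID-5 is also the only outcome for which the SAP states blinded assessment (Section 3, Randomization). If its event definition stays open, it may be settled after the data have been seen. The chi-square test leaves baseline information unused and gives no estimate of the difference, although Section 4 plans 95% confidence intervals.

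**Working it through.** **The plan's own figure.** The only sample-size calculation is for PHQ-SADS. With an effect size of 0.4, two-sided 5% and 80% power, 2 × (1.960 + 0.842)² / 0.4² = 98.1, so 99 per arm; the t-test gives 99.1, so 100 per arm. The stated 200 reproduces. The SAP gives no event rate, effect or power for the SCID-5. All rates below are therefore assumptions, chosen to show direction and range. Power is the normal-approximation two-proportion figure at two-sided 5%.

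**Step 1: disorders that ended before randomisation.** Let q be the share of each arm that scores present on past disorder alone, and let p be the rate after randomisation, taken to be the same with or without such a history. The observed rate is q + (1 − q) × p, so the difference is multiplied by (1 − q). With p = 30% (SOM) and 15% (MBSR), and 100 per arm:

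| q | SOM | MBSR | Difference (points) | Power |
|---|---|---|---|---|
| 0 | 30.0% | 15.0% | 15.0 | 72% |
| 0.10 | 37.0% | 23.5% | 13.5 | 55% |
| 0.30 | 51.0% | 40.5% | 10.5 | 32% |
| 0.50 | 65.0% | 57.5% | 7.5 | 19% |

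Both arms gain the same kind of event, so the effect is dilution and not bias between arms.

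**Step 2: disorders present at entry.** Let b be the share with a disorder at entry. Current status at T4 is b × persistence + (1 − b) × onset. Occurrence since baseline is b + (1 − b) × onset. Take 99 per arm (110 less 10%), b = 25%, and onset 15% (SOM) and 9% (MBSR).

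Occurrence since baseline:

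- SOM: 0.25 + 0.75 × 0.15 = 36.25%
- MBSR: 0.25 + 0.75 × 0.09 = 31.75%
- Difference 4.5 points, power 10%, whatever the persistence.

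Current status, with 75% persistence in SOM: 0.25 × 0.75 + 0.75 × 0.15 = 30.0%. The MBSR rate depends on its assumed persistence:

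| Persistence, MBSR | MBSR rate | Difference (points) | Power |
|---|---|---|---|
| 75% | 25.5% | 4.5 | 10% |
| 65% | 23.0% | 7.0 | 20% |
| 55% | 20.5% | 9.5 | 34% |
| 45% | 18.0% | 12.0 | 51% |

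The advantage of current status runs from nothing to large and comes entirely from the assumed effect on recovery.

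**Step 3: can the order reverse?** Take b = 15%, persistence 60% in both arms, onset 30% and 15%, half of new cases remitted by T4, and 99 per arm.

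- Current status: 0.15 × 0.60 + 0.85 × 0.30 × 0.5 = 21.75% against 0.15 × 0.60 + 0.85 × 0.15 × 0.5 = 15.4%. Difference 6.4 points, power 21%.
- Occurrence since baseline: 0.15 + 0.85 × 0.30 = 40.5% against 0.15 + 0.85 × 0.15 = 27.75%. Difference 12.75 points, power 47%.

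Here occurrence since baseline gives the larger contrast.

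**The case against.** The strongest defence is that the SAP permits a reading as current diagnosis. Both II.1 and the outcome definition refer to 7-month follow-up, the analysis section ties the interview to T4, and the score is present or absent. On that reading, recovered cases score absent and disorders that ended before randomisation are not counted. The reading is open, but the definition calls the assessment retrospective, which favours a look-back, and the SAP does not choose.

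Second, the SAP's introductory text presents the training as preventive, and for prevention, occurrence over follow-up is a natural outcome. This stands. Choosing between current status and occurrence since randomisation is a choice of estimand, and Step 3 shows that current status is not always the more sensitive one. It does not justify counting episodes that were over before randomisation.

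Third, a protocol or interview manual may set the window. That is possible, but the SAP's own outcome definition and question II.1 would still need to agree.

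A reader might infer more: that anyone ill at entry must score present, that recovery is therefore invisible, and that a true effect will be lost. The documents do not support this. They do not fix the window at baseline, and the loss in Step 2 vanishes when persistence is equal. The 50–70% in Section 3, Sample size, is a figure for symptom levels in healthcare workers, so it cannot serve as the share of participants with a diagnosis at entry.

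**Conclusion.** The point holds as a mismatch between definition and question, together with an avoidable weakness in the test. The retrospective definition has no lower limit and can count disorders that treatment cannot affect. This can dilute the comparison in II.1; it gives no reason to expect bias between arms.

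The size cannot be stated from the SAP. Under Step 1's assumptions the difference shrinks in proportion to the share counted on past disorder alone: by a tenth at q = 0.10 and by half at q = 0.50. For disorders present at entry, neither the size nor the direction is settled, so certain dilution is not shown and neither post-randomisation definition is shown to be better on power. The outcome is secondary and carries no power claim. The reason to act is that its event definition should be fixed before analysis, at little cost.

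**What to change.** In Section 6, Outcome definitions, state a SCID-5 reference period that matches II.1 and starts no earlier than randomisation. One workable form is:

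- Tested outcome: criteria for any listed disorder met at the T4 interview.
- Reported alongside: occurrence since randomisation, by arm, stating whether a disorder already present at randomisation counts.
- In both: disorders that ended before randomisation are not counted.

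In Section 6, Analysis methods, replace the chi-square test with a logistic regression of presence on group, adjusted for T0 PHQ-SADS, and report the marginal risk difference with its 95% confidence interval. Every randomised participant has this covariate, because Section 6, Missing data, says randomisation required a completed T0. The adjustment uses baseline information; it does not undo the counting of past disorders, so both changes are needed.

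The cost is SAP wording, a coding rule, slightly more analysis work and fewer counted events than under an open look-back. No extra assessment is needed, provided the interview records whether a disorder is current and when past episodes ended.

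### The primary PHQ-SADS analysis uses T4 scores only, so participants without a T4 questionnaire do not contribute to an analysis labelled ITT, and no missing-data assumption or prespecified check is given for it

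*SAP*

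**What the plan says.** Section 6, Treatment effects at T4, places the primary analysis on the ITT sample and states: "ANCOVA will be used to examine the main effect (PHQ-SADS) of the intervention at T4". A linear mixed model is then brought in for one reason, expected differences between starting cohorts. Its terms are group, baseline and cohort. There is no time term, no participant effect and no T2 or T3 outcome.

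Section 4, Analysis populations: "The intention-to-treat population will include all randomized patients, according to the treatment they were randomized to receive".

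Section 3, Sample size, expects loss: "To overcome attrition, we will increase the size of our groups with 10" per cent. Section 3, Trial design, says that control participants "will be able to participate in an adapted MBSR intervention after they completed the study (7 months").

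Section 6, Course to treatment effect at T4, is a separate model: "The course of treatment effects from baseline to T4 for both primary and secondary outcomes" are evaluated at T2, T3 and T4. Here, and only here, the SAP says: "Restricted maximum likelihood will be used as estimation method to handle missing data". The effect size reported from this model comes from "dividing the adjusted group difference between the pooled means (T2, T3, T4) by the pooled standard deviations at T0", which is an average over the three times.

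Section 6, Missing data: "No imputation will be needed for baseline measures, because participants were only randomized if T0 was completed". The rest of that section notes that the online platform forces an answer to each item, and expects few missing data on that ground. The planned sensitivity analyses are a per-protocol analysis and a further, unnamed one that depends on the missing-value patterns seen. The flow diagram in Section 5 has entries for losses to follow-up and for people randomized but left out of the primary analysis, both with reasons. Losses are summarized by arm.

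**The concern.** With one outcome row per participant, a mixed model with a cohort effect behaves like ANCOVA: someone without T4 drops out of the group contrast, and REML recovers nothing from that person's T2 and T3 scores. Forced item entry prevents skipped items but not a questionnaire that is never returned. The primary estimate is thus complete-case by its specification, although the SAP does not say so or state the assumption under which that is valid.

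Two things are at stake. First, if people leave before T4 because of how they scored at T2 or T3, and this happens at a different rate or in a different way in the two arms, the estimate is biased even though the data that would correct it have been collected. Second, because no missing-data check is fixed in advance, the choice between the T4-only result, the course model's T4 contrast and imputation would be made after the data are seen.

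**Working it through.** **1. The plan's own figures.** For d = 0.4, two-sided alpha 0.05 and 80% power, the t-test needs 99.08 per arm, so 100 per arm or 200, as stated. 200 × 1.10 = 220, as stated. At 10% loss, 220 × 0.10 = 22 have no T4 score and 198 (99 per arm) are analysed. Power at 99 per arm is 80% by t-test, and 90% by ANCOVA if the correlation with baseline is 0.5. Power is therefore not the problem.

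**2. Scale.** The SAP equates a 5-point difference with d = 0.4, which implies SD = 5 / 0.4 = 12.5.

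**3. Assumptions, none of them in the SAP.** Correlation 0.5 between baseline and each follow-up and 0.65 between follow-ups; true effect −5 points; log-odds of T4 dropout 0.7 per SD of the score that drives it, with higher scorers leaving; dropout rates by arm as listed. Bias is measured against the full-data ANCOVA in large simulated samples (600,000 per arm).

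**4. Standard error of the T4-only contrast.** SE = 12.5 × √(1 − 0.5²) × √(1/n1 + 1/n2). With 99 and 99 this is 12.5 × 0.866 × 0.1421 = 1.54. It is also 1.54 at 12%/8% and 15%/5%, 1.56 at 15%/10% and 1.59 at 20%/10%.

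**5. Dropout driven by the T3 score, same slope in both arms** (last row: slope in MBSR only).

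| Loss, MBSR/control | T4-only bias, points | Bias / SE | Type I error |
|---|---|---|---|
| 10%/10% | 0 | 0 | 5.0% |
| 12%/8% | 0.13 | 0.08 | 5.1% |
| 15%/10% | 0.16 | 0.10 | 5.1% |
| 20%/10% | 0.32 | 0.20 | 5.5% |
| 15%/5% | 0.33 | 0.21 | 5.5% |
| 10%/10%, one-arm mechanism | 0.34 | 0.22 | about 5.5% |

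Every non-zero bias favours MBSR, because more distressed people leave and loss is higher, or score-dependent only, in the MBSR arm. If the imbalance were reversed, so would be the sign. An estimator that also uses T2 and T3 has no bias in these rows. That is by construction, since it conditions on the score that drives dropout and treats T2 and T3 as always observed.

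**6. Other mechanisms.** If dropout depends on baseline only, both estimators are unbiased. If it depends on the unseen T4 score itself (missing not at random), both are unbiased at 10%/10%. At 15%/10% the bias is about 0.30 (T4-only) and 0.19 (with T2 and T3); at 15%/5% it is about 0.6 and 0.4. Using T2 and T3 reduces this bias but does not remove it.

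**7. Precision.** Under the assumed correlations, R² for T4 is 0.25 from baseline and 0.53 from baseline, T2 and T3. At 10% loss, SE = 12.5 × √[(0.47/0.9 + 0.28) × 2/110] = 1.51, against 1.54. The gain is small.

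**8. Can the course model be used as it stands?** The SAP does not say that time is categorical. It combines ARH(1) with random intercepts and slopes. At three occasions there are 6 distinct variances and covariances. ARH(1) uses 4 parameters (3 variances, 1 correlation). A participant random intercept and slope with their covariance add 3, so 7 parameters for 6 quantities (numerical rank 6): not identified. Without that covariance it is 6 for 6, which is saturated.

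**The case against.** The strongest reply is that a baseline-adjusted T4 ANCOVA is a legitimate primary analysis, and that the bias is zero at the only attrition figure in the SAP if both arms lose people at the same rate and in the same way. Every non-zero figure above rests on assumed correlations, slopes and rates by arm. The course model already analyses PHQ-SADS at T2, T3 and T4 by REML, and the flow diagram already discloses exclusions and losses by arm. All of this stands, and it holds the severity down. It does not supply a stated assumption for the primary estimate, a named T4 contrast, or a missing-data check fixed in advance.

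Three stronger readings are tempting and not supported:

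- **That the ITT label makes the primary analysis invalid or conceals exclusions.** Section 4 defines ITT by allocation, and Section 5 openly provides for randomized participants missing from the primary analysis. The fault is an unstated assumption and unused data.
- **That the later offer of MBSR to controls shows the result will be biased.** It is an incentive to stay, so a reason for unequal rates. It is no evidence that dropout depends on scores differently in the two arms, and the SAP gives no rates by arm.
- **That the bias could be large.** With correlations of 0.6, a slope of 1 per SD and mechanisms in opposite directions in the two arms, bias reaches about 1.1 points at 20% loss and 1.5 at 30%. Nothing in the SAP supports such mechanisms, and both rates exceed its 10%.

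The objection is also right that the course model cannot simply be promoted to primary as written (step 8).

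**Conclusion.** The point holds, at minor to moderate severity. By its specification the primary analysis omits randomized participants without T4, and leaves their T2 and T3 scores unused. The REML statement does not reach it, and the only missing-data sensitivity analysis is to be chosen after the patterns are seen. The estimate is valid if T4 missingness depends only on baseline, arm and cohort. Otherwise the likely distortion at about the planned attrition runs from nothing to roughly a third of a point, against a target difference of 5 points. The gap in prespecification does not depend on those assumptions; the size of the bias does.

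**What to change.** Preferred: take the primary estimate as the T4 group contrast from a T2 to T4 PHQ-SADS mixed model with categorical time, group, group × time, baseline and a cohort random effect. Use an unstructured within-participant covariance in place of ARH(1) plus participant random intercept and slope. Multiple imputation of T4 from T2 and T3, done by arm, is an alternative. State the missing-at-random assumption, keep the T4-only ANCOVA as the named sensitivity analysis, and report by arm how many participants have no T2 to T4 score.

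Minimum, if the ANCOVA stays primary: state its missing-data assumption and name the T4 contrast from the model above as the prespecified missing-data sensitivity analysis.

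In either case, name one delta-shift analysis in advance for data missing not at random, in place of the open-ended wording. For scale, a 5-point shift for 10% of one arm moves the estimate by 5 × 0.10 = 0.5 points, or 0.5 / 1.54 = 0.32 SE.

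Cost: SAP wording and slightly more modelling, with no new data. Downsides are reliance on missing at random, little gain in precision, no gain for participants with no follow-up score, less benefit if those who miss T4 also miss T3, and bias from data missing not at random that is reduced but not removed.
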